## Sample size

The sample size will be estimated based on the SUPRE-MISS study that evaluated the effectiveness of BIC in suicide attempters that visited the emergency department. Centres recruit a minimum of 1730 subjects (865 per treatment group) considering a significance level of 95% (two-sided), power of 80% and assuming 3% suicides in the TAU and 1% in the BIC group at 18-months follow-up.

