## II. BIC RCT Study

### Trial design

The study will be a multicenter randomized (1:1) control trial (RCT). Enrolment including eligibility screening and randomization into either the intervention or control group will be conducted according to the WHO randomization methods. Suicide attempters assigned to the COVID-19 BIC group will receive in-person motivational and awareness increasing interview using the COVID-19 BIC method (Annex 1) described separately. These interviews will be conducted by trained health care professionals (eg: a doctor, a nurse, a psychiatrist, a psychologist) one day before or on the day of discharge. The training for the health care professionals will be given on a social media platform where a group training will take place.

Baseline assessments will be conducted after randomization and last follow-up will be 18-month post intervention with intermediate follow-ups by online trained volunteers (eg: volunteers from NGOs, individuals working with mental health, community workers, medical students, research assistants) at the 1, 2, 4, 8, and 12 weeks and then at 4, 6, 12, and 18 months.

A back-up supervisory system will be established to support the health care professionals as well as for the volunteers if they encounter any problems during the interview or during the follow-ups.

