### Participants

All suicide attempters who visit the emergency department and meet the inclusion criteria during a 12-month period will be asked to participate in the study.

*Suicide attempt* is defined as a nonfatal self-directed potentially injurious behavior with any intent to die as a result of the behavior. A suicide attempt may or may not result in injury. Suicide attempters will be diagnosed according to the ICD-10 as well as a score of 2 or above on the Medical Damage Scale (MDS) (5).

The number of participants for each of the site can be determined based on the catchment area, but the emergency department of the study unit should serve at least a population of 250,000. This

estimate was adopted from the MONSUE study, A European Multicentre Study on Suicidal Behaviour (6).

Each site in the respective country is requested to translate instruments used in this study into the local language. All suicide attempters will be included in the analysis, but a separate analysis will be conducted by stratifying suicide attempters according to their different MDS score.

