#### *Inclusion criteria*

Participants are eligible to participate in the study if they fulfill the following inclusion criteria:

- aged 15 or above;  
(**optional:** Each centre has the option to recruit suicide attempters below the age of 15. However, the instruments need to be adopted for the respective age group. Parental consent might be needed for suicide attempters younger than 15 and in some countries younger than 18 to participate in the study).
- attempted suicide who are admitted to the emergency department during the 12-months study period
- proficient in the local language
- consent to participate

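### The stated 80% power is for 865 per group with known 18-month outcomes, but 865 is given as the number to recruit; the significance level and the scope of 1730 also need correcting

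*Protocol*

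**What the plan says.** The Sample size section fixes the number, the level and the power in one sentence: "Centres recruit a minimum of 1730 subjects (865 per treatment group) considering a significance level of 95% (two-sided), power of 80" per cent, "assuming 3% suicides in the TAU and 1% in the BIC group at 18-months follow-up". It names no test, no continuity correction and no allowance for participants whose outcome at 18 months cannot be established. No other section gives an expected loss rate.

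Three other places bear on it:

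- **Trial design:** "The study will be a multicenter randomized (1:1) control trial (RCT"), so the two groups are equal in size.
- **Participants and Inclusion criteria:** "The number of participants for each of the site can be determined based on the catchment area", with a minimum catchment population of 250,000, and recruitment is of those who "attempted suicide who are admitted to the emergency department during the 12-months study period".
- **Treatment as Usual and Evaluation Procedures:** control participants are contacted once, at 18 months, while the intervention group has nine contacts. An alternative contact person, for patients who cannot be reached, is described only under BIC Intervention.

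**The concern.** A sample size formula returns the number of participants who must contribute an outcome. Here that number appears as the number to recruit, in a trial with an 18-month endpoint and a single contact in the control group. If some outcomes stay unknown, the power is lower than a reader of the sentence would take it to be. The outcome is rare: about 26 suicides (865 × 0.03) against 9 (865 × 0.01) are expected, so there are few events to lose.

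Two wording faults sit in the same sentence. A significance level of 95% is not a usable type I error rate. And a minimum recruited by centres can be read as a figure for each centre or for all together, while the Participants section leaves each site's number open. A site cannot tell from the text what total it is contributing to.

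**Working it through.** **Inputs from the protocol.** p1 = 0.03 and p2 = 0.01 (Sample size), difference d = 0.02; equal groups (Trial design); power 80%; two-sided. The level is read as 5%, since the printed 95% can only be the confidence level. The mean proportion is 0.02.

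**Step 1: reproduce 865.** The uncorrected size is

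n = [z(0.975)·√(2 × 0.02 × 0.98) + z(0.80)·√(0.03 × 0.97 + 0.01 × 0.99)]² / d²

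= [1.960 × √0.0392 + 0.842 × √0.0390]² / 0.0004

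= (0.3881 + 0.1662)² / 0.0004 = 768.0 per group.

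With continuity correction,

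n' = (n/4)·[1 + √(1 + 4/(n·d))]² = (768.0/4)·[1 + √(1 + 4/15.36)]² = 865.1 per group.

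This is the protocol's figure (2 × 865 = 1730). Power by the same formula at 865 is 79.99%. The other usual variants do not give 865: uncorrected pooled 769 after rounding up, unpooled 766, arcsine 718, one-sided uncorrected 605, one-sided corrected 702. The formula that matches has no term for unknown outcomes.

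**Step 2: power when some outcomes are unknown.** The loss rate is an assumption, shown as a range. It is taken as equal in the two groups and unrelated to outcome. With 865 recruited per group and a share *u* unknown, 865 × (1 − u) remain. Exact power sums the binomial probabilities of all outcome pairs that the test rejects at two-sided 5%.

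| Unknown (assumed) | Known per group | Continuity-corrected formula | Fisher, exact power | Uncorrected chi-square, exact power |
|---|---|---|---|---|
| 0% | 865 | 80.0% | 82.1% | 86.7% |
| 10% | 778 | 75.1% | 77.2% | 82.9% |
| 20% | 692 | 69.4% | 72.3% | 78.3% |
| 30% | 606 | 62.6% | 65.0% | 72.7% |

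**Step 3: where 80% is lost.**

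- Fisher: 80.05% at 826 per group (4.5% loss) and 79.8% at 822 (5.0% loss), so the limit is just under 5%.
- Uncorrected chi-square: 80.2% at 725 (16.2% loss) and 79.9% at 720 (16.8% loss), so the limit is about 16%. The approximate formula is stricter: 769 are needed, and 1 − 769/865 = 11%.
- Continuity-corrected formula: no reserve at all.

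**Step 4: the scope of 1730.** If it were a minimum for each centre, a centre at the smallest allowed catchment would need 1730 / 250,000 = 692 participants per 100,000 residents within the 12-month recruitment period. That makes the trial total the more natural reading, but the sentence does not state it.

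**The case against.** The strongest reply is that the stated figure is arithmetically right and that no shortfall is shown. The protocol names no test. Evaluated exactly, neither Fisher's test nor the uncorrected chi-square test needs complete follow-up: power at 865 is 82.1% or 86.7%. The continuity correction is inferred from the match, and 769 / (1 − 0.112) also gives about 866, so an unstated allowance of about 11% on the uncorrected size cannot be ruled out. The figure of 1730 is called a minimum. Suicide death can be established without reaching the participant, and an alternative contact is recorded. The choice of test and the handling of unknown outcomes may sit in an analysis plan that is not shown.

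Much of this stands. A reader might infer that the 80% is a miscalculation, or that any loss at all takes power below 80%. The documents do not support either: the figure reproduces, and exact power leaves a small to moderate reserve depending on the test. What remains is that the protocol itself fixes a recruited number and a power and does not state the condition that links them. The alternative contact is described only for the intervention group, so its reach in the control group is unclear.

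A reader might also infer that the loose reference to centres lowers the power. It does not: 1730 as the trial total gives the stated power, and 1730 per centre would give more in the pooled trial. Nor does low power within a single country count against this plan. Comparing countries is a listed objective, but the only hypothesis stated is the overall one, and no powered country-level test is planned.

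**Conclusion.** The point holds as a fault of statement, not of arithmetic. The 865 per group is the continuity-corrected requirement for known outcomes, and presenting it as the recruitment number makes the 80% conditional on nearly complete ascertainment at 18 months. The size depends on two things the protocol does not give, the test and the share of unknown outcomes. Over an assumed 10 to 30% loss, power is about 77 to 65% with Fisher's test and 83 to 73% with the uncorrected chi-square test. With loss below about 5% (Fisher) or 16% (chi-square) there is no shortfall. Unequal or outcome-related loss would add bias, which these figures do not cover.

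The significance level of 95% is wrong as written, although the intended 5% is clear from the reproduction. The scope of 1730 is unclear and should be settled against the Participants section. Both are wording defects, and neither changes the power.

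**What to change.** Rewrite the Sample size section along these lines, once the sponsor has confirmed the scope of 1730:

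> The two-sided significance level is 5%. With suicide by 18 months assumed to be 3% under TAU and 1% under BIC, 865 participants per group with a known 18-month outcome give 80% power by the continuity-corrected two-proportion formula. The trial will recruit at least 1730 participants in total over all centres. If 10%, 20% or 30% of outcomes are unknown, power with [the test to be used] is about [77%, 72%, 65% for Fisher's exact test; 83%, 78%, 73% for the uncorrected chi-square test].

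Keep only the figures for the test that will be used, so that the power quoted and the analysis refer to the same procedure. If the sponsor did build in an allowance for loss, state it here instead, with the test it goes with.

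The sponsor should also reconcile the total with the site-determined numbers in the Participants section and with the 12-month recruitment period. Which of these governs recruitment is a design decision and is not prejudged here.

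Cost: text only. The stated power becomes slightly less favourable, and no extra patients are required.

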## BIC Intervention

[figure not shown]
The intervention, including the educational session at discharge and the follow-up procedures, remains unchanged. All participants will receive the BIC intervention in addition to TAU, which is described in the next section. The BIC intervention will include nine follow-ups post discharge (1,2,4, 8, 12 weeks and at 4,6,12 months) with a final 18-months follow-up. Even though, the BIC is a brief one time one-hour motivational awareness increasing interview, there are regular follow-ups of up to 18-months which is a long follow-up.

The BIC intervention will include:

- A. *time of discharge:* an hour individual educational motivational awareness increasing session as close to the time of discharge as possible (the day before or the day of discharge). The information session includes the following:
- ✓ suicidal behavior as a sign of psychological/social distress
  - ✓ risk factors and protective factors
  - ✓ basic epidemiology of suicide and suicide attempt
  - ✓ alternative coping mechanisms instead of destructive behaviours
  - ✓ referrals for treatment or social support

Along with this educational motivational and awareness increasing session, patients will receive two pamphlets highlighting suicide prevention methods and risk factors for suicide (Annex 2- supplied later on).

A. *after discharge*: nine follow-ups via phone calls, physical visits, messaging or using tele-medicine (depending on the site) at:

The follow-ups will be conducted by a volunteer (eg: volunteers from NGOs, individuals working with mental health, community workers, medical students, research assistants), and these volunteers will receive training as well. Follow-ups can be either by phone call, physical visits, tele-medicine or messaging. If a center has the capacity and opportunity to do tele-medicine, tele-medicine should be the preferred follow-up method according to the WHO recommendation. An alternative contact person (eg: a friend or a spouse) who will be knowledgeable about the suicide attempter's outcome and situation will be recorded in case volunteers are unable to reach the patient.

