### Primary Outcome

Hypothesis: The BIC will significantly lead to a reduced death by suicide at 18-months follow-up than treatment as usual.

Outcome measure: death from suicide at 18-month follow-up

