There will be follow-up contacts at nine timepoints for those in the intervention group and one follow-up at 18-month for those in the control group. These follow-ups will be conducted using a questionnaire template (Annex 3) and will follow-up if the participant is still live, any consequent suicide attempt, and the well-being of the participant.

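### The 865 per group matches the number needed with a known 18-month outcome but is set as the number to recruit, so the stated 80% power has little or no margin for loss to follow-up

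*Protocol*

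**What the plan says.** The Sample size section sets the recruitment figure and ties the power to it: "Centres recruit a minimum of 1730 subjects (865 per treatment group) considering a significance level of 95% (two-sided), power of 80" per cent, "assuming 3% suicides in the TAU and 1% in the BIC group at 18-months follow-up". A significance level of 95% can only mean a two-sided alpha of 0.05. Under Trial design, allocation is 1:1.

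The endpoint is fixed under Primary Outcome: "Outcome measure: death from suicide at 18-month follow-up".

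Three places bear on how that outcome becomes known:

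- BIC Intervention provides for recording another person who knows how the participant is faring, "in case volunteers are unable to reach the patient".
- Evaluation procedures gives the intervention group nine contacts, and "one follow-up at 18-month for those in the control group". Whether the participant is alive is one of the things these contacts establish.
- Treatment as Usual likewise places the control follow-up at 18 months after discharge.

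The protocol gives no expected loss rate, no inflation factor and no separate number of evaluable participants.

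**The concern.** A sample size formula for two proportions returns the number of participants whose outcome is known. If that number is used unchanged as the number to recruit, the stated power assumes that every outcome is obtained. Here the outcome is read 18 months after discharge in people recruited in emergency departments after a suicide attempt, and the protocol itself foresees that some cannot be reached.

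The comparison rests on few events. At 865 per group the assumed rates give 0.03 × 865 = 26.0 and 0.01 × 865 = 8.7 suicides, about 35 in all. If outcomes are missing, a null result would be read as coming from a trial with 80% power when the power was lower. The point concerns the stated power only.

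**Working it through.** **Inputs** (Sample size; Trial design): p1 = 0.03 (TAU), p2 = 0.01 (BIC), difference δ = 0.02, mean p̄ = 0.02, alpha 0.05 two-sided (z = 1.960), power 80% (z = 0.8416), allocation 1:1. Loss rates are not in the protocol. The range of 0 to 30% is an assumption.

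**Step 1: reproduce 865.**

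Uncorrected: m = [1.960·√(2·0.02·0.98) + 0.8416·√(0.03·0.97 + 0.01·0.99)]² / 0.02² = [1.960·0.1980 + 0.8416·0.1975]² / 0.0004 = (0.3881 + 0.1662)² / 0.0004 = 768.0.

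Continuity-corrected: n = (m/4)·[1 + √(1 + 4/(mδ))]² = 192.0·[1 + √(1 + 4/15.36)]² = 192.0·(2.1227)² = 865.1.

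The printed 865 is this value, or 866 if rounded up. Other variants do not reproduce it: uncorrected pooled 769 (rounded up), unpooled 766, arcsine 719, one-sided 605 (702 corrected), 90% power 1028.

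**Step 2: power by the same formula after loss.** Inverting the correction gives m = (n − 1/δ)²/n = (n − 50)²/n. Power is then Φ[(0.02·√m − 0.3881)/0.1975].

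| Assumed loss | Known per group | m | Power |
|---|---|---|---|
| 0% | 865 | 767.9 | 80.0% |
| 10% | 778 | 681.2 | 75.1% |
| 20% | 692 | 595.6 | 69.4% |
| 30% | 606 | 510.1 | 62.6% |

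**Step 3: exact power by test.** The protocol names no test, and the formula is only an approximation. Summing the binomial probabilities over all tables that each test rejects gives:

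| Assumed loss | Fisher's exact | Uncorrected chi-square |
|---|---|---|
| 0% | 82.1% | 86.7% |
| 5% | 79.8% | 84.9% |
| 10% | 77.2% | 82.9% |
| 15% | 74.3% | 80.7% |
| 20% | 72.3% | 78.3% |
| 30% | 65.0% | 72.7% |

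The continuity-corrected chi-square has exact power 82.1% at no loss and 79.8% at 5% loss. So power drops below 80% at just under 5% loss for Fisher's test or the corrected chi-square, and between 15% and 20% loss for the uncorrected chi-square.

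**Step 4: is the uncorrected test's extra power bought with a raised error rate?** For 606 to 865 per group and common risks of 1% to 3%, its exact two-sided level is about 4.3% to 5.1%. The corrected test runs at 2.2% to 3.5%. The gain comes almost wholly from removing conservatism.

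**The case against.** A reader might infer that 80% power is gone as soon as anyone is lost, or that it holds only with complete follow-up. That is literally true only of the normal-approximation formula that reproduces 865. Exact power at 865 per group is 82.1% or 86.7% depending on the test, so some loss can be absorbed. This objection stands and limits the claim to little or no margin.

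The basis of 865 is also inferred. Reading it as 769 inflated for about 11% loss fits arithmetically (769/0.89 = 864.04, rounded up to 865). Nothing in the text mentions such an allowance, however, and the corrected formula reaches 865.1 directly.

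A reader might further infer that every unreachable patient is a lost outcome. The protocol does not support that. The alternative contact is recorded precisely so that someone else can report on the participant, and for a death endpoint such a person may supply the answer. But no yield is given, and the arrangement is described under the BIC intervention without being clearly extended to controls, who have a single contact. It can reduce loss; it does not justify an implicit rate of zero. The protocol describes no other source of vital status, but it does not exclude one either.

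The figure of 1730 is a minimum, so more may be recruited. No larger target is given, though, and the 80% is attached to 1730.

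Finally, the choice of test may properly be left to a statistical analysis plan, and its absence from the protocol is not criticised here. The protocol does, however, fix both a recruitment number and a power, and these two need to agree.

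**Conclusion.** The point holds in limited form. The recruitment minimum of 865 per group coincides with the number needed with a known outcome, and no allowance for loss is stated. The arithmetic behind 865 is sound; what is missing is the step from participants analysed to participants recruited.

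On the basis that reproduces the figure, power falls by about 5, 11 and 17 percentage points at 10, 20 and 30% loss. With the most favourable test examined it stays above 80% at 15% loss and is below it at 20%. The actual shortfall is unknown, because every loss rate used is an assumption, applied equally to both arms, and the formula is inferred. A reader might also infer bias from the unequal number of contacts; this calculation does not address that and supports no such conclusion. The trial is not invalidated, but its stated power should be corrected.

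**What to change.** In the Sample size section:

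1. Label 865 per group as the number with known 18-month vital status.
2. State the loss expected in each arm, taking account of what the alternative contact is expected to recover and whether it applies to controls.
3. Restate the power that 865 recruited per group gives at that loss, computed for the test that will be used.

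The power figures must belong to one test. If the continuity-corrected basis is kept, the figures are about 75, 69 and 63% at 10, 20 and 30% loss. If an uncorrected chi-square is chosen, print its own figures (about 83, 78 and 73%). The two sets must not be mixed. The choice itself can be made in the statistical analysis plan, provided the sample size text agrees with it.

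The cost is a wording change and a slightly less favourable power statement. No extra patients are required. Should the sponsor prefer to keep 865 per group with known outcome, recruitment would be 865/(1 − loss): 865/0.90 = 962 per group at 10% loss, or 865/0.80 = 1082 at 20%, both rounded up.
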